## Pretreatment Evaluation

All patients will have a history and physical examination as part of their admission to Grady Memorial Hospital. All patients will have a panorex xray or maxillofacial CT scan to assess the severity and location of mandible fractures and other facial fractures, as is the standard of care. In addition to routine blood tests (complete blood count and metabolic panel), patients reporting diabetes in their history will have a hemoglobin A1c drawn. Patients reporting human immunodeficiency virus infection in their history will have a CD4 count drawn unless they have recent result (CD4 count within 6 months) or

refuse. This will allow the level of immunocompetence in patients with known diabetes or HIV to be evaluated and additional medical care (additional antibiotics, antifungals, opportunistic infection prophylaxis, strict blood glucose control etc.) to be provided as the standard of care.

### Registration and Randomization

Eligible patients will be offered the opportunity to enroll in the study when they are first consulted by the oral and maxillofacial surgery service. Consent will be obtained by one of the study investigators. Subjects will then be randomized to either Stryker hybrid arch bars or Erich archbars group using sealed envelopes that have been prepared by the study statistician.

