**Schema:**

Consecutive patients presenting to Grady Memorial Hospital with mandibular fractures will be evaluated for recruitment in this pilot study. Patients requiring either open reduction and internal fixation (ORIF) or closed reduction (CR) will be included in the study.

The choice of surgical method (ORIF versus CR) will be determined by the patient preference in conjunction with the attending surgeons expert opinion. The surgical procedure for closed treatment is a simple and standardized procedure involving placement of arch bars and maxillomandibular fixation (MMF) for a period of 4-6 weeks. The surgical procedure for ORIF will involve the placement of arch bars intraoperatively, exposure of fractures by intraoral or transcutaneous incisions, intraoperative MMF and ORIF. All procedures will be done under a general anesthesia. All eligible subjects will be initially stratified to ORIF or CR. Subjects within each group will then be randomized to either Stryker Hybrid arch bars or Erich arch bars (control). In all groups the arch bars will be left in place for six weeks. Stryker Hybrid arch bars will be placed according to the manufacturers instruction using a minimum of four locking screws per arch. Erich arch bars will be placed using a combination of 24 and 25 gauge wire as is the historical technique. Arch bar removal is a simple procedure that will be completed under local anesthesia in the outpatient clinic.

The primary predictor variable is the type of archbar (Stryker Hybrid versus Erich). The primary outcome variable is time required to place the arch bars. Secondary outcomes include union (nonunion, fibrous union, malunion), complications, hospital charges and need for additional procedures

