### Therapy

In the ORIF group, thirty patients will be randomized to each arm of the study (30 Stryker hybrid arch bars and 30 Erich arch bars). In the CR group, twenty subjects will be randomized to each arm of the study (20 Stryker hybrid arch bars and 20 Erich arch bars). A number of different resident surgeons will perform the surgical treatment including the application of MMF. All residents will complete Stryker clinical skills training and will be standardized as the application process and technique for both arch bar systems. For all study subjects, time will be recorded from start to completion of maxillary and mandibular arch bar placement, and from insertion of throat pack to removal of throat pack. This will be measured using two different electronic timers to record the respective times. All arch bars will be left in place (ORIF and CR) for a period of 6 weeks. Patients will be discharged from the hospital as soon as possible after medically stable from surgery. Patients will be seen for follow up routinely for a minimum of 6 weeks postoperatively to ensure appropriate healing.

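### No step requires the operating resident to be assigned before the arch bar allocation is revealed, and the randomisation section neither times the envelope opening nor repeats the stratify-first order

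*Protocol*

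**What the plan says.** **Order of stratification and allocation.** The protocol's Schema states: "All eligible subjects will be initially stratified to ORIF or CR". Bar type is randomised afterwards, within each group. The Therapy section agrees and fixes the split: "In the ORIF group, thirty patients will be randomized to each arm of the study", with twenty per arm in the CR group. The choice between ORIF and CR is not randomised; it "will be determined by the patient preference in conjunction with the attending surgeons expert opinion".

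**How allocation is carried out.** The Registration and Randomization section is the only one that describes the mechanism. On timing it says: "Eligible patients will be offered the opportunity to enroll in the study when they are first consulted by the oral and maxillofacial surgery service". An investigator then takes consent, and next: "Subjects will then be randomized to either Stryker hybrid arch bars or Erich archbars group using sealed envelopes". The section names no stratum, no separate envelope series, no recording step and no time of opening.

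**Who operates.** The Therapy section says: "A number of different resident surgeons will perform the surgical treatment including the application of MMF". It adds that all residents are trained by the manufacturer and standardised in technique for both systems. It does not say when, by whom or on what basis a resident is assigned to a case.

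**What is recorded and analysed.** The operative variables listed under Patient Assessment are application time, surgical time and surgical approach; the operator is not among them. The SAP compares application time between arms by t-test, follows this with regression on stepwise-selected covariates, and analyses by original assignment. It names no operator covariate.

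**The concern.** The primary endpoint is a duration produced by the operator. If the bar type is known when the case is given to a resident, the assignment can follow it. A more experienced resident might be given whichever system is thought harder, or a resident keen on one system might take those cases. The direction cannot be predicted, so the effect could favour either arm.

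The arms would then differ in who applied the bars as well as in which bar was applied, and the estimated difference in application time would mix the two. This is performance bias. Intention-to-treat analysis does not correct it, because it keeps patients in their assigned arm without changing who operated on them. With the operator absent from the listed variables and from the SAP, the problem might also go unseen.

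A second, smaller matter is that the working instruction for randomisation leaves out the stratify-first step. Someone following that section alone could open an envelope before the ORIF/CR decision had been written down. An early opening would also allow patients to be randomised who never reach surgery and so have no application time.

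**Working it through.** The plan states no figure to reproduce on this point. The Sample size section says that no prior studies guide the calculation and gives no effect size, standard deviation or power. The arm sizes are consistent: 30 + 30 = 60 ORIF, 20 + 20 = 40 CR, 100 in total, so 30 + 20 = 50 per bar type.

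**Step 1: what is fixed before allocation?**

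| Choice | Schema and Therapy | Registration and Randomization |
|---|---|---|
| ORIF or CR | Set before bar type is randomised | Not mentioned |
| Operating resident | Several residents; no assignment rule | Not mentioned |
| Time of opening the envelope | Not stated | After consent; no time given |

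The ORIF/CR order is planned but missing from the operative section. The resident is not fixed before allocation anywhere.

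**Step 2: size in minutes.** Both inputs are assumptions.

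Bias = (difference between arms in the share of cases done by slower residents) × (extra minutes those residents need).

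- 10-point difference, 10 minutes slower: 0.10 × 10 = 1 minute.
- 20-point difference, 10 minutes slower: 0.20 × 10 = 2 minutes.

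The difference in share here is systematic, meaning that it arises because the allocation was known. Chance imbalance in residents is a separate matter and is covered by the standard error.

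**Step 3: effect on the 5% error rate.** The documents give no standard deviation, so a speed gap of 0.5 to 1.0 SD and a share difference of 10 to 30 points are assumed. With 50 per arm the standard error of the difference is √(2/50) = 0.20 SD. The test is taken as two-sided (the SAP does not state sidedness), and error = Φ(b/0.20 − 1.96) + Φ(−b/0.20 − 1.96), where b is the bias in SD.

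| Share difference | Speed gap | Bias b | Actual error |
|---|---|---|---|
| 0.10 | 0.5 SD | 0.05 SD | 5.7% |
| 0.10 | 1.0 SD | 0.10 SD | 7.9% |
| 0.20 | 0.5 SD | 0.10 SD | 7.9% |
| 0.20 | 1.0 SD | 0.20 SD | 17.0% |
| 0.30 | 0.5 SD | 0.15 SD | 11.7% |
| 0.30 | 1.0 SD | 0.30 SD | 32.3% |

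The minute scale and the SD scale are separate illustrations; nothing in the documents links them.

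**The case against.** **The ORIF/CR choice is already placed first.** A reader of the randomisation section alone might infer that nothing fixes this choice before allocation. The documents do not support that. The Schema stratifies first, and the per-stratum splits in Therapy can be guaranteed only if the stratum is known when the envelope is drawn. What stands is an omission: the operative section does not repeat the order or ask for the decision to be recorded.

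**The envelope is not tied to first consult.** A reader might infer that it is. The section ties only the enrolment offer to first consult and gives no opening time. Early opening is therefore possible but not prescribed.

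**Randomisation is not undone.** A reader might infer that the arms stop being comparable. They do not: patients are compared as assigned, and a later choice of operator does not alter their baseline comparability. The risk is a difference in how the treatment was delivered.

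**Residents are trained on both systems.** This is the strongest point against a large effect, since it should narrow the speed gap between residents. It does not stop cases being assigned with the allocation in view.

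**The magnitude is assumed.** This is correct. Without a standard deviation or target difference, no one can say from the documents whether 1 to 2 minutes is material. For the same reason, no figure is offered for movement between ORIF and CR. The documents give no time gap between the procedures, and such a figure would concern total surgical time, a secondary outcome.

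**Conclusion.** The point holds for the operator, and as a wording gap for the stratum. No section requires the resident to be assigned before the bar type is known, the operator is not a listed variable or a named covariate, and the primary outcome depends on the operator. That leaves an open route to performance bias in the primary comparison.

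Under the assumed inputs the bias is 1 to 2 minutes, or 0.05 to 0.30 SD on the wider assumptions, which would take a nominal 5% error to about 6% to 32%. These figures show what selective assignment could do. They are not evidence that it occurred. If residents are assigned without regard to bar type, this bias is zero.

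The data collection sheet was not available for this review, so the operator may be recorded there. That would help in detecting the problem but would not prevent it. The change is worth making because it closes the route at little cost.

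**What to change.** Amend Registration and Randomization along these lines:

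> After consent, the ORIF/CR decision (as in the Schema) and the operating resident are written on the data collection sheet. The next envelope from that stratum's series is then opened in the operating room, immediately before arch bar placement. Subjects are analysed in the recorded stratum and assigned arm even if the procedure or the resident later changes. Any change of resident is recorded, and resident is reported by arm.

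This brings the section into line with the Schema and Therapy. It also limits losses between randomisation and surgery, since a consented patient who never reaches the operating room is not randomised.

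**Cost.** Protocol wording, an entry for the resident on the data sheet if it has none, both bar sets available in theatre for each case, and two envelope series instead of one.

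**If envelopes have already been opened.** The SAP is written in the past tense, so the amendment may come too late for some or all subjects. In that case, document when each envelope was opened relative to the ORIF/CR decision and the assignment of the resident, and report resident and stratum by arm where they were recorded.

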### Sample size

No prior studies exist to guide sample size calculations. It is anticipated that this pilot study will include a total of 40 subjects in the CR arms and 60 subjects in the ORIF arms. This study will allow for a drop out rate 30% for the outcome variables which is consistent with the patient population based on prior studies.

### Therapy

In the ORIF group, thirty patients will be randomized to each arm of the study (30 Stryker hybrid arch bars and 30 Erich arch bars). In the CR group, twenty subjects will be randomized to each arm of the study (20 Stryker hybrid arch bars and 20 Erich arch bars). A number of different resident surgeons will perform the surgical treatment including the application of MMF. All residents will complete Stryker clinical skills training and will be standardized as the application process and technique for both arch bar systems. For all study subjects, time will be recorded from start to completion of maxillary and mandibular arch bar placement, and from insertion of throat pack to removal of throat pack. This will be measured using two different electronic timers to record the respective times. All arch bars will be left in place (ORIF and CR) for a period of 6 weeks. Patients will be discharged from the hospital as soon as possible after medically stable from surgery. Patients will be seen for follow up routinely for a minimum of 6 weeks postoperatively to ensure appropriate healing.

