**Introduction:**

Mandible fractures are commonly a result of maxillofacial trauma and account for the majority of facial fractures. The majority of fractures are treated with either ORIF or CR. Erich arch bars are the most commonly used type of MMF and are considered the gold standard. However, the application of Erich arch bars is time-consuming and requires the presence of teeth. Intermaxillary fixation screws and IVY loops are alternative approaches that may also be used. The hybrid arch bar system developed by Stryker is unique in that the bars are secured to the underlying alveolar bone with self-drilling locking screws rather than the teeth. This potentially reduces the time required to place the arch bars as well as the need for teeth.

There are no studies comparing Stryker Hybrid arch bars to traditional methods of MMF.

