### Patient Assessment

Patients will be assessed during surgery and in the postoperative period while in the hospital. After discharge, patients will be followed routinely to ensure complete bony consolidation of the fracture and at 4 to 12 weeks postoperatively. The primary

outcome variable is application time for placement of arch bars. Secondary outcomes include intra-operative surgical time length of stay after surgical procedure, length of stay, hospital charges, fracture healing and complications.

All data will be collected by the PI or CI during the initial admission for surgery to repair the fracture or at the one week and 6 week follow-up appointments. All data will be recorded on a standard data collection sheet. Subjects will have not have any questionnaires or surveys to complete. Demographic, preoperative, operative and postoperative variables will be recorded and analyzed. Demographic data includes age, sex and race. Preoperative variables include medical history (DM and HIV), social history, fracture location, number of fractures, time from injury to surgery and antibiotic use. Operative variables include time for arch bar application, surgical time and surgical approach. Post operative variables include fracture healing, follow-up, complications and hospital charges. It is anticipated that the study will conclude at 24 months. All subjects will be paid \$50 at the 4 to 12 week follow-up visit.

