### Data Collection

A data collection sheet will be used to record demographic, preoperative, operative and postoperative variables. A separate copy of the data collection sheet is attached. All data collection sheets (unscrubbed and scrubbed) will be kept in a locked office. All data will be entered into a computer and this will be both password protected and secured in a locked office.

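### Low-severity improvement: analyse application time in one fixed model with treatment and the ORIF/CR stratum, plus operator if it was recorded; the gain is mainly precision

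*Protocol*

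**What the plan says.** **Who does the timed task.** Protocol, Therapy: "A number of different resident surgeons will perform the surgical treatment including the application of MMF". The same section adds "All residents will complete Stryker clinical skills training and will be standardized as the application process and technique for both arch bar systems". It does not give the number of residents, their experience, or how they are assigned to cases.

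**Stratification.** Protocol, Schema: "All eligible subjects will be initially stratified to ORIF or CR". Device is then randomised within each group, 30:30 in ORIF and 20:20 in CR (Therapy).

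**What is recorded.** Protocol, Patient Assessment: "Operative variables include time for arch bar application, surgical time and surgical approach". The wording leaves the list open. Data Collection says "A separate copy of the data collection sheet is attached", but the sheet is not in the text supplied.

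**Analysis.** The SAP, dated November 2018 and written in the past tense, does four relevant things:
- It compares preoperative and operative variables between arms.
- It compares application time across those variables, using correlation for age and t-tests or one-way analysis of variance for the others.
- It compares application time between arms by t-test.
- It fits a multiple regression with covariates picked by stepwise selection.

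No covariate is named for that regression. The SAP does not say whether the t-test or the regression is the main result.

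**Size.** Protocol, Sample size: "No prior studies exist to guide sample size calculations". The plan is that "this pilot study will include a total of 40 subjects in the CR arms and 60 subjects in the ORIF arms". No effect size, SD or power target is given.

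**The concern.** Application time measures operator performance as well as the device. If residents differ in speed, or if placement takes longer in one surgical group than the other, that variation goes into the error term of an unadjusted t-test and widens the interval for the device effect. The stratification factor is known for every patient and was built into the randomisation, yet the analysis is not committed to using it. Stepwise selection lets the data decide which covariates enter, so the adjusted estimate is not fixed in advance.

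In a pilot with no stated power target, the width of the interval for the time difference is the most relevant measure of what the trial delivers. At stake is some of that precision, together with a clear statement of which analysis is the main one.

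**Working it through.** **Plan's own figure.** 2 × (30 + 20) = 100, which agrees with 60 ORIF + 40 CR. With no effect size or SD in the documents, no power calculation can be reproduced. Application time is measured during surgery, so the 30% drop-out allowance should matter little, and 50 per arm is used throughout.

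**Assumptions, none from the documents.** Two-sided 5% level; total within-stratum SD of 1; 8 or 12 residents; one operator per case; operator independent of arm; operator share of variance (ICC) 0.05, 0.2 or 0.4.

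**Baseline.** The t-test interval has width of about 2 × 1.98 × √(2/50) = 0.79 SD. The difference detectable with 80% power is (1.96 + 0.84) × √(2/50) = 0.56 SD.

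**Ceiling on the operator gain.** If operator were removed at no cost, the width would shrink by the factor √(1 − ICC):
- ICC 0.05: √0.95 = 0.975, or 2.5% narrower.
- ICC 0.2: √0.80 = 0.894, or 10.6% narrower.
- ICC 0.4: √0.60 = 0.775, or 22.5% narrower.

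The real gain is smaller, because a few operators show less than the full variance and are unevenly spread over the arms by chance.

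**Simulation.** 6,000 runs per cell, 30+30 ORIF and 20+20 CR, no ORIF/CR mean difference. The comparison is the t-test against a random operator intercept (REML) plus stratum.

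| Operators | ICC | Mean width, t-test | Mean width, random intercept | Ratio | Power at 0.5 SD, t-test → random intercept |
|---|---|---|---|---|---|
| 8 | 0.05 | 0.790 | 0.779 | 0.986 | 0.704 → 0.717 |
| 12 | 0.05 | 0.788 | 0.779 | 0.989 | 0.699 → 0.709 |
| 8 | 0.2 | 0.780 | 0.725 | 0.929 | 0.702 → 0.756 |
| 12 | 0.2 | 0.784 | 0.732 | 0.934 | 0.702 → 0.764 |
| 8 | 0.4 | 0.767 | 0.634 | 0.827 | 0.730 → 0.876 |
| 12 | 0.4 | 0.778 | 0.644 | 0.828 | 0.717 → 0.865 |

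The interval is therefore about 1%, 7% and 17% narrower. At a true effect of 0.8 SD, the power gain is at most 2.2 points (0.977 → 0.999). At 1.0 SD every model has power of 0.996 or more.

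**Validity of the t-test.** In the same cells its type I error is 4.6% to 5.4%, so leaving operator out does no harm when operator is independent of arm.

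**Stratum term alone.** With shares 0.6 and 0.4 and an assumed ORIF/CR difference of 0.5 SD, the variance between strata is 0.6 × 0.4 × 0.5² = 0.06. The t-test works with variance 1.06 and the stratified model with 1.00. The ratio of widths is √(1/1.06) = 0.971, about 3% narrower; the simulated ratio was 0.97. If the two groups take equal time, the gain is zero.

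**Choice of operator term.** At ICC 0.05, fixed operator effects give widths of 0.803 (8 operators) and 0.820 (12), wider than the t-test's 0.790 and 0.788. Power at 0.5 SD falls from 0.704 to 0.696 and from 0.699 to 0.670. The random intercept showed no such loss.

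**A limit on the operator term.** If the device effect itself varies between residents (assumed interaction variance 0.1, ICC 0.2), the t-test's error rate for inference to operators in general is about 11% with 5 operators and 8% with 10. A fixed main-effect operator term leaves it at 12% and 9%. A random intercept is also a main-effect term, so it does not address this either.

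**The case against.** The case against acting is substantial. Using several residents trained on both systems is a legitimate choice. Patients are randomised individually, and the t-test is valid if operator is independent of arm. The documents set no precision or power target, and the ICC, the number of residents and the effect size above are all assumed. The Introduction says that "the application of Erich arch bars is time-consuming and requires the presence of teeth", so the device effect may be large, and at 0.8 SD or more the power gain is negligible. Operator may be a field on the data sheet. If so, the SAP's comparison of application time across operative variables may already examine it, and it could be a stepwise candidate. Surgical approach is a listed operative variable and may stand for ORIF/CR, although it may mean only the incision route. The past tense of the SAP suggests that the analysis may be complete.

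Most of this stands, and it is why the point is of low severity. Three things remain:
- The stratification factor is known without the data sheet, and the SAP does not commit to it in the model.
- Comparing application time across operative variables one at a time describes those variables; it does not give an adjusted device effect.
- The interval narrows at any effect size, and fixing the covariates avoids data-driven selection.

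A reader might infer that who placed the bars was never recorded. The documents do not support that: the list of variables is open and the sheet was not available.

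**Conclusion.** The point holds as a low-severity improvement and not as an error. The SAP names neither the ORIF/CR stratum nor the operator in its analysis of application time. With operator independent of arm, the cost is mainly precision: about 1%, 7% or 17% of interval width at assumed ICC 0.05, 0.2 or 0.4. For the stratum term alone it is about 3% if ORIF and CR times differ by an assumed 0.5 SD, and nothing if they are equal. If residents hardly differ, there is no real gain from the operator term.

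A reader might go further and infer that the time comparison is biased because residents were matched to devices. No passage shows that, and training every resident on both systems points away from it. Nor is it ruled out, since nothing says how residents are assigned or whether the resident is fixed before the envelope is opened. An operator-by-arm table would help settle it.

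The statement that the t-test is valid covers the average effect among the participating residents. It does not extend to operators in general if the device effect differs between residents.

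**What to change.** Make the main analysis of application time one linear model fixed in advance, with treatment and the ORIF/CR stratum, in place of the unadjusted t-test and stepwise selection. State whether operator was recorded. If it was, add it as a random intercept (not as fixed effects) and report an operator-by-arm table. If the SAP comparison has already been run, keep it and report this model beside it as a declared added analysis. If operator cannot be recovered, fit treatment plus stratum and state the limitation.

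The cost is one model, one table and, at most, one or two data fields. The downsides are that operator may not be recoverable for finished cases, that a single operator per case is assumed although the Protocol does not say one resident places both arches, and that the operator term does not deal with a device effect that differs between residents.

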## Objectives

- 1) Is there a difference in the application time when comparing Stryker hybrid arch bars to Erich arch bars for the ORIF or CR of mandibular fractures?
- 2) Is there any difference in overall surgical time, postoperative length of stay, hospital charges, fracture healing or complications when comparing Stryker hybrid arch bars to Erich arch bars for the ORIF or CR of mandibular fractures?

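### Length of surgery is compared with no prespecified adjustment for ORIF/CR or other facial fractures, which costs avoidable precision in a secondary outcome

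*Protocol*

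**What the plan says.** Protocol, Therapy, defines two timed intervals. One covers arch bar placement; the other runs "from insertion of throat pack to removal of throat pack". Each has its own clock: "This will be measured using two different electronic timers to record the respective times". The second interval is not labelled overall surgical time, but it is the only candidate for that quantity.

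The primary "outcome variable is application time for placement of arch bars". The second objective asks "Is there any difference in overall surgical time, postoperative length of stay, hospital charges" and more, and Patient Assessment repeats surgical time, stay and charges as secondary outcomes.

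Pretreatment Evaluation has imaging done "to assess the severity and location of mandible fractures and other facial fractures, as is the standard of care". The inclusion list does not require an isolated mandible fracture, and none of the six exclusions concerns other facial fractures or concurrent procedures.

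Patient Assessment lists fracture location and number of fractures among the preoperative variables, without saying whether non-mandibular fractures count. On the operative side: "Operative variables include time for arch bar application, surgical time and surgical approach". Neither list names other facial fractures or other procedures. The attached data collection sheet is not in the text available for this review.

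The SAP tests length of surgery between devices by t-test. It then mentions multiple regression on covariates chosen stepwise, naming neither the outcome modelled nor the candidates. It gives no analysis of stay or charges. Patients are stratified by ORIF or CR before randomisation (Protocol, Schema), but the t-test does not use this.

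**The concern.** The throat-pack interval counts everything done between its two end points. If a patient has another facial fracture repaired in the same session, that time enters the outcome although it has nothing to do with the arch bar. Randomisation balances such patients between devices only on average, and with 50 per device the chance differences are not negligible. The ORIF/CR split is a second known source of spread, and the unadjusted t-test leaves it in the error term despite the stratified design.

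At stake is the precision of one of the named secondary comparisons, and the ability to rule out an obvious alternative explanation if the devices appear to differ in surgical time.

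**Working it through.** The documents give no SD, effect size or power, so there is no stated calculation to reproduce. The arm totals agree: 30 + 30 + 20 + 20 = 100, or 50 per device. Surgical time is captured in theatre, so the 30% dropout allowance should not reduce its sample size.

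**Assumed inputs (not in the documents).** A share q of patients, 10% to 30%, has an added repair of fixed length A, 60 to 120 minutes. The SD of surgical time is otherwise 60 minutes. Alpha is two-sided 0.05; the SAP gives 0.05 without sidedness.

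**Step 1: reference precision.** With no added repairs, SE = 60 × √(2/50) = 12 minutes. The difference detectable with 80% power is (1.96 + 0.84) × 12 ≈ 34 minutes, or 0.56 SD.

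**Step 2: upper bound on the loss.** Added repairs independent of device multiply the variance by 1 + q(1−q)A²/SD². Perfect adjustment would remove all of the excess. The last two columns take a true difference of 0.56 SD.

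| q | A (min) | Variance ratio | SE ratio | Unadjusted SE (min) | Power | N per device for 80% |
|---|---|---|---|---|---|---|
| 10% | 60 | 1 + 0.09 × 1 = 1.09 | 1.044 | 12.5 | 76.5% | 55 |
| 20% | 90 | 1 + 0.16 × 2.25 = 1.36 | 1.166 | 14.0 | 67% | 68 |
| 30% | 120 | 1 + 0.21 × 4 = 1.84 | 1.356 | 16.3 | 54% | 92 |

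For repairs lasting only half an SD (30 minutes), power stays at 78% or more even at q = 30%.

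**Step 3: what an imaging indicator recovers.** A fracture seen on imaging is not the same as a fracture repaired. Keep the central case (20% repaired, 90 minutes), and assume 40% have another facial fracture and half of these are repaired.

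- Repair variance: 0.2 × 0.8 = 0.16 A².
- Part explained by the indicator: 0.4 × 0.6 × 0.5² = 0.06 A², leaving 0.10 A².
- With A²/SD² = 2.25, the unadjusted variance ratio is 1 + 0.16 × 2.25 = 1.36 and the adjusted ratio is 1 + 0.10 × 2.25 = 1.225.
- SE ratio: √(1.36/1.225) = 1.054, so the unadjusted SE is about 5% larger, not 17%.

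Variable repair length would lower this further.

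**Step 4: chance imbalance.** At q = 20%, the difference in counts between two groups of 50 has SD √(2 × 50 × 0.16) = 4 patients. A difference of 5 or more has probability about 0.26 (continuity-corrected normal: 4.5/4 = 1.125). Five patients at 90 minutes shift the mean difference by 5 × 90/50 = 9 minutes. This is the same variance as in Step 2, not an additional harm: 4 × 90/50 = 7.2 minutes, and √(12² + 7.2²) = 14.0.

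**Step 5: ORIF/CR.** With a 60:40 split and ORIF lasting k within-stratum SDs longer than CR (k assumed), the pooled variance used by the t-test is multiplied by about 1 + 0.6 × 0.4 × k². That is 1.24 at k = 1 and 1.96 at k = 2, so the reported SE is 11% or 40% larger than one from a model with the stratum term. Allocation is balanced within strata, so the t-test is conservative here rather than biased.

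**The case against.** The strongest reply is that the SAP does provide for adjustment: fracture number and location are recorded, and stepwise selection could bring them into a regression. This stands in part. It would be wrong to say that nothing is adjusted for. But the SAP does not say that the regression concerns length of surgery, the candidates are unnamed, and the recorded fracture count may be mandibular only. Partial adjustment is possible, not planned. Nor can it be said that the data sheet lacks the item, since the sheet is not in the text.

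Second, same-session repair is an inference. The protocol says that other facial fractures are looked for, not that they are repaired in the same operation, how often, or for how long. This stands, and it is why the size is given as a range whose low end is small.

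Third, a reader might infer that removing this noise would let the trial detect the few minutes that a faster arch bar could save. It would not. Under the assumed SD the standard error is 12 minutes with no other repairs at all, and the 9-minute shift in Step 4 is smaller than that.

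Fourth, a reader might infer that the throat-pack definition also distorts stay and charges. It bears on surgical time only. For stay and charges the point is just that concomitant injuries are neither excluded nor a named covariate, and the larger gap is that the SAP has no analysis of either.

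**Conclusion.** The point holds as a modest one about precision. Surgical time takes in any other repair done in the session, other facial fractures are expected and admitted, and neither they nor ORIF/CR have a prespecified place in the comparison of length of surgery.

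Under the assumed inputs, other repairs make the unadjusted standard error at most 4% to 36% larger than under perfect adjustment. An imaging indicator recovers less, about 5% in the central case. The true size cannot be fixed from the documents.

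Two stronger readings are not supported. A reader might infer systematic bias between devices, but concomitant fractures are independent of a randomised allocation, so the t-test remains valid. A reader might also infer that the primary outcome is contaminated, but arch bar placement has its own timer and does not contain these repairs. The change is worthwhile because it is nearly free, not because a main conclusion depends on it.

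**What to change.** - Record whether another facial fracture is present on preoperative imaging (yes/no), if the data sheet does not already do so. The imaging is standard of care, so the item can also be taken from existing records. Allocation cannot affect it, so adjusting for it brings in no post-treatment variable.
- Replace the t-test for length of surgery with a prespecified linear model containing treatment, ORIF/CR and this indicator.
- Use the same covariates in whatever analysis of stay and charges is adopted.
- Add a sensitivity analysis restricted to isolated mandible fractures.

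The SAP is written in the past tense. If the analysis has already been run, report the model as an additional analysis and label it so.

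The cost is one data item and slightly more analysis work. Eligibility, recruitment, treatment and the primary outcome are unchanged.
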